10.13 APPENDIX 13: ABBREVIATIONS

ADC:	anti-body drug conjugate
ADL:	activities of dialy living
AE:	adverse event
AESI:	adverse event of special interest
ALK:	anaplastic lymphoma kinase
ALT:	alanine aminotransferase
ART:	antiretroviral therapy
AST:	aspartate aminotransferase
ATA:	anti-therapeutic antibodies
BOR:	best overall response
BSA:	body surface area
CEA:	carcinoembryonic antigen
CEACAM5:	carcinoembryonic antigen-related cell adhesion molecule 5
CI:	confidence interval
COVID-19:	coronavirus disease-2019
CR:	complete response
CSICF:	Core Study Informed Consent Form
CT:	computed tomography
CYP450:	cytochrome P450
DCR:	disease control rate
DOR:	duration of response
ECG:	electrocardiogram
eCOA:	electronic clinical outcome assessment
ECOG:	Eastern Cooperative Oncology Group
eCRF:	electronic case report form

Property of the Sanofi group - strictly confidential

Clinical Trial Protoco SAR408701-ACT172	ol 27- 241 - tusamitamab ravtansine Ver	Sep-2021 rsion number: 1
eGFR:	estimated glomerular filtration	rate
EGFR:	epidermal growth factor recept	tor
EOT:	end-of-treatment	
FDG-PET:	fluorodeoxyglucose-positron e	mission tomography
FIH:	first in human	
G-CSF:	Granulocyte colony stimulating	g factor
GDPR:	General Data Protection Regul	ations
HIV:	human immunodeficiency viru	IS
HRT:	hormone replacement therapy	
IB:	Investigator's Brochure	
ICF:	informed consent form	
ICH-GCP:	International Conference on Ha	armonisation- Good Clinical Practice
ICI:	immune checkpoint inhibitor	
IEC:	Independent Ethics Committee	es
IHC:	immunohistochemistry	
IMP:	investigational medicinal produ	uct
IRB:	Institutional Review Board	
IRR:	infusion-related rate	
IRT:	interactive response technology	У
IV:	intravenous infusion	
MRI:	magnetic resonance imaging	
NCI-CTCAE:	National Cancer Institute- Con	nmon Terminology Criteria for Adverse Events
NE:	not evaluable	
NIMP:	noninvestigational medicinal p	product
NSCLC-SAQ:	Non-Small-Cell Lung Cancer S	Symptom Assessment Questionnaire
NSQ NSCLC:	non-squamous non-small-cell	lung cancer
NTR:	narrow therapeutic range	
ORR:	objective response rate	
PCSA:	potentially clinically significant	nt abnormality
PD:	progressive disease	
PD-1:	programmed death-1	
PD-L1:	programmed death ligand-1	
PFS:	progression-free survival	
PGIC-LCS:	patient global impression of ch	ange-lung cancer symptom
PGIS-LCS:	patient global impression of se	eventy-lung cancer symptom
PK:	pharmacokinetics	
PR:	partial response	
PRO:	patient-reported outcome	
Q2W:	every 2 weeks	
QTL:	quality tolerance limit	
RBC:	red blood cells	0.111
RECIST:	Response Evaluation Criteria i	n Solid Tumours
RUSI:	KUS receptor tyrosine kinase	l
SAE:	serious adverse event	
SAP:	statistical analysis plan	
SD:	stable disease	

Property of the Sanofi group - strictly confidential

Clinical Trial Protocol SAR408701-ACT17241 - tusamitamab ravtansine 27-Sep-2021 Version number: 1

SoA:	schedule of activities
SUSAR:	suspected unexpected serious adverse reaction
TEAE:	treatment-emergent adverse event
ULN:	upper limit of normal
WBC:	white blood cells
WOCBP:	woman of childbearing potential

1 INTRODUCTION

There are no major changes to the analyses described in the protocol.

1.1 STUDY DESIGN

This is a single group, Phase 2, open-label, multi-center study assessing efficacy (anti-tumor activity), safety, and PK of tusamitamab ravtansine single agent in NSQ NSCLC participants with negative (ie, intensity 1+ whatever the percentage of stained tumor cells or <1% of tumor cells) or moderate (ie, intensity \geq 2+ in \geq 1% and <50% of tumor cells) CEACAM5 expression tumors and high circulating CEA (\geq 100 ng/mL) at baseline.

During the pre-screening phase, participants who were pre-screened failed in the EFC15858 Phase 3 trial with available CEACAM5 status (central assessment by immunohistochemistry, IHC) as negative or moderate expression on archival tumor tissue can be pre-screened for ACT17241 study. Participants with high circulating CEA (≥100 ng/mL) will be screened and will go through protocol screening procedures.

This study is designed to obtain preliminary efficacy, safety and PK data on tusamitamab ravtansine administered as monotherapy at 100 mg/m² Q2W to participants with NSQ NSCLC tumors with CEACAM5 moderate-negative tumor expression and high circulating CEA levels.

Approximately 285 participants will be pre-screened to achieve approximately 38 treated participants, based on an estimated pre-screening failure rate of 84% and an estimated study screening failure rate of 15%.

The cycle duration is 2 weeks. The median expected duration of study per participant is estimated as 40 weeks: up to 4 weeks for screening, a median of 24 weeks for treatment, and a median of 12 weeks for end of treatment assessments and the safety follow-up visit. Enrolled participants may receive study intervention until disease progression, unacceptable AE, initiation of a new anticancer therapy, or the participant's or Investigator's decision to stop the treatment, whichever comes first.

1.2 OBJECTIVES AND ENDPOINTS

Objectives	Endpoints
Primary	
 To assess the anti-tumor activity of tusamitamab ravtansine when given every 2 weeks (Q2W) in non-squamous non-small-cell-lung-cancer (NSQ NSCLC) participants with negative or moderate CEACAM5 expression tumors and high circulating carcinoembryonic antigen (CEA) levels 	 Objective Response Rate (ORR) of tusamitamab ravtansine, defined as the proportion of participants who have a confirmed complete response (CR) or partial response (PR) as best overall response (BOR) per Response Evaluation Criteria In Solid Tumors (RECIST) v1.1

Table 1 - Objectives and endpoints

Property of the Sanofi group - strictly confidential

	Objectives	Endpoints
Secor	ndary	
•	To assess the safety and tolerability of tusamitamab ravtansine	 Incidence of participants with treatment-emergent adverse events (TEAEs), serious adverse events (SAEs) and laboratory abnormalities according to the National Cancer Institute (NCI) Common Terminology Criteria for Adverse Events (CTCAE) v5.0
•	To assess other efficacy parameters of tusamitamab ravtansine	 Progression-free survival (PFS), defined as the time from the date of first tusamitamab ravtansine administration to the date of the first documented disease progression or death due to any cause, whichever comes first.
		 Disease control rate (DCR), defined as the percentage of participants who have achieved confirmed CR or PR, or stable disease as BOR per RECIST v1.1
		 Duration of response (DOR), defined as the time from first documented evidence of CR or PR until progressive disease (PD) determined per RECIST v1.1 or death from any cause, whichever occurs first
•	To evaluate the immunogenicity of tusamitamab ravtansine	 Incidence of participants with anti-therapeutic antibodies (ATAs) against tusamitamab ravtansine
•	To document the pharmacokinetics (PK) of tusamitamab ravtansine	Tusamitamab ravtansine concentrations
Fertia	ıry	
•	To evaluate patient-reported outcomes (PROs)	 Time to deterioration in the overall severity of disease-related symptoms (cough, pain, dyspnea, fatigue, appetite) as measured by the NSCLC- Symptom Assessment Questionnaire (SAQ)
		 Patient global impression of severity (PGIS) and patient global impression of change (PGIC) in disease-related symptoms will be measured by generic PGIS lung cancer symptom (PGIS-LCS) and PGIC lung cancer symptom (PGIC-LCS) scales
		 Change from baseline in overall side effect impact as measured by the Functional Assessments of Cancer Therapy Item GP-5 (FACT-GP5)
•	To explore modulations of circulating CEA as a potential pharmacodynamic biomarker of response to tusamitamab ravtansine treatment and to evaluate circulating CEA levels at pre-screening and its correlation with CEACAM5 tumor expression on fresh biopsy (if available)	 Circulating CEA at pre-screening, screening, during the treatment period and during the follow-up period; tumor CEACAM5 expression (on fresh biopsy tumor sample, if available)
•	To explore the relationship between CEACAM5 expression in archived and fresh biopsy at screening (if available)	 CEACAM5 expression on archived and fresh biops at screening
•	To explore the relationship between the tumor mutation profiles detected in the circulating free DNA (cfDNA) at baseline with efficacy outcome	Mutation analysis for tumor cfDNA at baseline

Property of the Sanofi group - strictly confidential

1.2.1 Estimands

Primary estimand defined for primary efficacy endpoint is summarized in below Table 2. More details are provided in Section 3.

For this estimand, the study intervention of interest will be SAR408701.

Endpoint	Estimands			
Category (estimand)	Endpoint	Population	Intercurrent event(s) handling strategy	Population-level summary (Analysis and missing data handling)
Primary objective: To circulating CEA level		ity of tusamitamab ravta	ansine Q2W in NSCLC participants with negative or n	noderate CEACAM5 expression tumors and high
Primary endpoint (primary estimand)	Confirmed objective response (confirmed CR or PR as BOR), determined according to RECIST v1.1	All-treated population	Regardless of investigational medicinal product IMP discontinuation (treatment policy strategy) Based on tumor assessments done before initiation of further anticancer therapy ("while not initiating anticancer therapy" strategy)	Objective response rate defined as rate of participants with confirmed objective response and two-sided 95% confidence interval (CI) using the Clopper-Pearson method. In the absence of confirmed objective response, participants will be considered as non-responders, whatever the reason (including participants with non evaluable BOR).

Table 2 - Summary of primary estimand for main endpoints

2 ANALYSIS POPULATIONS

The following populations for analyses are defined:

Population	Description	
Pre-screened	All participants who signed the pre-screening informed consent.	
Screened	All participants who signed the screening informed consent for study participation	
Enrolled	All participants from screened population who have been allocated to intervention regardless of whether the intervention was received or not.	
All-treated	All enrolled participants exposed to the study treatment, regardless of the amount of treatment administered. All safety analyses will be performed on this population, which is also the primary population for analysis of all efficacy parameters.	
Activity	All-treated participants who have measurable disease at study entry and at least 1 postbaseline evaluable tumor assessment. Participants with no postbaseline evaluable tumor assessment but with an early clinical progression or who died from disease progression will also be included in this set. This population is the secondary population for analysis of efficacy parameters.	
РК	All participants from the all-treated population with at least 1 postbaseline PK concentration with adequate documentation of dosing and sampling dates and times.	
ATA	All participants from the all-treated population with at least 1 postbaseline ATA result (negative, positive, or inconclusive).	
Population without trial impact	All exposed participants:	
(disruption) due to COVID-19	 without any critical or major deviation related to COVID-19 	
	 and who did not permanently discontinue treatment due to COVID-19 	
	 and who did not permanently discontinue study due to COVID-19. 	

Table 3 -	Population	for analyses
-----------	------------	--------------

Abbreviations: ATA = anti-therapeutic antibody; PK = pharmacokinetic.

Note: In practice, a participant will be included in the enrolled population if the question "Will the subject continue in the treatment phase?" has been answered as "Yes" in the "Completion of screening phase" electronic case report form page.

In practice, a participant will be included in the enrolled population if the question "Will the subject continue in the treatment phase?" has been answered as "Yes" in the "Completion of screening phase" electronic case report form page.

Participants exposed to study intervention before or without being enrolled will not be considered enrolled and will not be included in any analysis population. The safety experience of these participants will be reported separately.

Enrolled participants for whom it is unclear whether they took the study intervention will be considered as exposed and will be included in the "all-treated" population.

For any participant enrolled more than once, only the data associated with the first enrollment will be used in any analysis population. The safety experience associated with any later enrollment will be reported separately.

Participants will be analyzed according to the intervention they actually received.

In practice, participants whose BOR is non-evaluable due to minimum criteria for SD duration not met (ie, overall response of SD and the minimum duration, defined as 0.75 x duration between the first IMP intake and the first planned tumor assessment is not met) and there is no subsequent evaluable tumor assessment, or documented PD after two or more non-evaluable tumor assessments (ie, overall response of PD and the time between the date of first IMP intake and the documentation of PD is greater than the theoretical planned date of the second tumor assessment) will be considered as not evaluable for the activity population.

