9.1 POPULATIONS FOR ANALYSES

The following populations for analyses are defined:

Population	Description
Pre-screened	All participants who signed the pre-screening informed consent.
Screened	All participants who signed the screening informed consent for study participation.
Enrolled	All participants from screened population who have been allocated to intervention regardless of whether the intervention was received or not.
All-treated	All enrolled participants exposed to the study treatment, regardless of the amount of treatment administered. All safety analyses will be performed on this population, which is also the primary population for analysis of all efficacy parameters.
Activity	All-treated participants who have measurable disease at study entry and at least 1 postbaseline evaluable tumor assessment. Participants with no postbaseline evaluable tumor assessment but with an early clinical progression or who died from disease progression will also be included in this set. This population is the secondary population for analysis of efficacy parameters.
РК	All participants from the all-treated population with at least 1 postbaseline PK concentration with adequate documentation of dosing and sampling dates and times.
АТА	All participants from the all-treated population with at least 1 postbaseline ATA result (negative, positive, or inconclusive).

Table 7 - Population for analyses

Abbreviations: ATA = anti-therapeutic antibody; PK = pharmacokinetic.

Note: In practice, a participant will be included in the enrolled population if the question "Will the subject continue in the treatment phase?" has been answered as "Yes" in the "Completion of screening phase" electronic case report form page.

Participants exposed to study intervention before or without being enrolled will not be considered enrolled and will not be included in any analysis population. The safety experience of these participants will be reported separately.

Enrolled participants for whom it is unclear whether they took the study intervention will be considered as exposed and will be included in the "all-treated" population.

For any participant enrolled more than once, only the data associated with the first enrollment will be used in any analysis population. The safety experience associated with any later enrollment will be reported separately.

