3.2.4 Supplementary analyses

The number (%) of participants within each BOR category, including not evaluable as per RECIST 1.1 and reason for being not evaluable will be provided for the all-treated population.

As a supplementary analysis, ORR as per RECIST v1.1 will also be summarized on the activity population (defined in Section 2). The same analytical approach as for the primary analysis defined in Section 3.2.2 will be used.

In addition, the best relative tumor change from baseline, defined as the smallest relative tumor change from baseline (where tumor change at time t is the difference between sum of the longest diameters of the target lesions at time t and baseline), will be summarized using a waterfall plot on the activity population (defined in Section 2).

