3.3.2.2.2 Disease control rate

Analysis of the DCR will be based on an estimand defined according to the following attributes:

- The endpoint is disease control response as per RECIST v1.1.
- The treatment condition of interest is tusamitamab ravtansine.
- The analysis population is the all-treated population (defined in Section 2).
- Intercurrent events:
 - The study intervention discontinuation intercurrent event will be handled with the treatment policy strategy. Disease control response will be assessed based on tumor assessments regardless of study intervention discontinuation,
 - The further anticancer therapy (including further systemic anticancer therapies) intercurrent event will be handled with the "while not initiating further anticancer therapy" strategy. Disease control response will be assessed based on tumor assessments done up to the initiation of further anticancer therapy.
- The population-level summary will be the DCR, defined as the rate of participants with disease control response and two-sided 95% CIs using the Clopper-Pearson method.

In the absence of disease control response before the analysis cut-off date (taking into account the intercurrent event handling strategies), participants will be considered as non-responders, whatever the reason (including participants with non-evaluable BOR).

As a supplementary analysis, DCR as per RECIST v1.1 will also be summarized on the activity population (defined in Section 2). The same analytical approach as described above will be used.

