3.8 INTERIM ANALYSES

An interim analysis for futility based on the number of confirmed objective responses observed in the activity population will be performed.

The study cut-off date for the interim analysis corresponds to the date on which the first 20 evaluable treated participants have had at least 2 postbaseline tumor assessments, experienced confirmed objective response, or have discontinued the study for any reason. For participants with 2 postbaseline tumor assessments and occurrence of response at the second postbaseline tumor assessment, the confirmatory assessment will also be included.

If 0 or 1 confirmed objective response is observed among the first 20 treated participants evaluable for anti-tumor activity, the enrollment will be stopped. Otherwise, the enrollment will continue with the 18 additional evaluable participants.

The study analysis will then be conducted in 2 steps.

The first step analysis will be conducted when all evaluable treated participants have had at least 2 postbaseline tumor assessments, experienced confirmed objective response, or have discontinued the study treatment for any reason. This study cut off can be up to approximately 20 weeks (16 weeks for 2 tumor assessments and 4 weeks for confirmation of response, if needed) after the last participant's first IMP administration. Of note, DCR will also be assessed at this cut-off.

The second step analysis for analysis of the secondary efficacy endpoints will be conducted approximately 4 months after the cut-off date for the primary analysis. At that time, the primary analysis for ORR and DCR will also be updated.

The final analysis will be conducted at the end of the study. Only safety analyses will be updated at this time.

For each analysis step, the analysis cut-off date will be defined as the date of the database extraction that will be performed for the analysis after the cut-off (study cut-off for the interim analysis, as well as the first and second analysis steps).

Analyses methods and conventions described in the other sections of this SAP will be applied for all analyses as applicable. The following additional rules will apply for analyses performed at interim analysis and at first analysis step:

- Participants without end of treatment visit performed at the time of the cut-off date will be considered as ongoing and exposed up to the cut-off date. Therefore:

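### SAP 2 narrows the activity population without declaring it, which can only hold or raise the supplementary ORR, and the first 20 at the interim have two unreconciled definitions

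*SAP*

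**What the plan says.** Protocol 9.1 (Table 7) defines the activity population as "All-treated participants who have measurable disease at study entry and at least 1 postbaseline evaluable tumor assessment". SAP Table 3 uses the same text and, like the protocol, adds a second route in: "Participants with no postbaseline evaluable tumor assessment but with an early clinical progression or who died from disease progression will also be included".

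The last paragraph of SAP 2 then declares two groups not evaluable for this population, in each case because BOR is non-evaluable:

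- (a) an overall response of SD before a minimum duration of 0.75 times the interval to the first planned scan, with no later evaluable scan;
- (b) "documented PD after two or more non-evaluable tumor assessments", which a parenthesis turns into a date test: time from first dose to PD "greater than the theoretical planned date of the second tumor assessment".

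Protocol 9.1 has no such removal. SAP 1 reports no major changes and SAP 3.9 is marked not applicable.

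The activity population is used for the supplementary ORR and the waterfall plot (SAP 3.2.4), the supplementary DCR (SAP 3.3.2.2.2) and the interim: "An interim analysis for futility based on the number of confirmed objective responses observed in the activity population will be performed". The stopping rule itself refers to the first 20 treated participants evaluable for anti-tumor activity. SAP 4 and Protocol 9.4 gloss that term, for the planned 38, as any postbaseline assessment, early clinical progression, or death due to progression.

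**The concern.** Both removed groups have a scan that was read, as SD or as PD. On the face of Table 3 they belong in the set, and the SAP treats each of them as a non-responder. Taking only non-responders out of a denominator moves the estimate in one direction. Group (b) is the harder to defend, because a documented progression is a clear treatment failure. The protocol does have a missed-scan rule, but it handles PFS and duration of response (Protocol 9.2.3.1 and 9.2.3.3) and removes nobody from a response rate.

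At stake are the supplementary ORR and DCR, the waterfall plot, and possibly the make-up of the 20 participants on whom the decision to continue enrollment rests. The study is open-label, with investigator-read scans and no data monitoring committee, so who counts should be settled before responses are counted.

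**Working it through.** **Inputs**

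- Scans every 8 weeks (56 days), window ±7 days: Protocol 8.1.
- SD minimum 0.75 × 56 = 42 days: SAP 2.
- Non-evaluable BOR counts as non-response for ORR (SAP 3.2.2) and DCR (SAP 3.3.2.2.2).
- 38 evaluable participants planned, 20 + 18; stop at 0 or 1 responses in 20: SAP 3.8 and SAP 4.
- Earlier cohort of 64: 13 PR and 28 SD (Protocol 2.1 and 4.3).
- Number removed, k: not in the documents. Assumed 1 to 3.

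**The plan's own figures.** 13/64 = 20.3% and 28/64 = 43.8% reproduce. The pre-screening number is 38/[(1 − 0.84)(1 − 0.15)] = 279.4, close to the stated 285; forward, 285 × 0.16 × 0.85 = 38.8. The plan gives no figure for the removals.

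**Direction.** With x responders among n and k non-responders removed, x/(n − k) ≥ x/n, with equality only when k = 0 or x = 0.

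**Size.** Scaling the earlier cohort to 38 gives 38 × 13/64 = 7.7 responders and 38 × 41/64 = 24.3 with disease control, so 8 and 24 are used; 4 responders is a lower case.

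| Successes | k = 0 (of 38) | k = 1 (of 37) | k = 2 (of 36) | k = 3 (of 35) |
|---|---|---|---|---|
| ORR, 4 | 10.5% | 10.8% | 11.1% | 11.4% |
| ORR, 8 | 21.1% | 21.6% | 22.2% | 22.9% |
| DCR, 24 | 63.2% | 64.9% | 66.7% | 68.6% |

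**Condition on the DCR row.** It holds under the SAP's 42-day minimum. The protocol states no minimum. If an early SD counted as control, removing one such participant would lower the rate: 24/38 = 63.2% to 23/37 = 62.2%.

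**Interim.** Without replacement the number of responses is unchanged. If the narrowed set selects the 20 and one removed non-responder's place goes to a later participant, compare P(X ≤ 1) = (1 − p)^n + n·p·(1 − p)^(n−1) at n = 19 (non-responder kept among the 20) and n = 20 (replaced), where p is the response rate in the others:

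| p | Kept | Replaced |
|---|---|---|
| 5% | 75.5% | 73.6% |
| 10% | 42.0% | 39.2% |
| 20.3% | 7.8% | 6.5% |

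The chance of stopping falls by about 1 to 3 points per replacement. If the SAP 4 gloss selects the 20, the change is zero.

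**Date test in (b).** The second scan is planned for day 2 × 56 = 112, with a window of day 105 to 119. Read literally with no window, PD on day 113 to 119 passes the test. That scan is on time, and a participant who missed only week 8 has one non-evaluable assessment, not two.

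**The case against.** The best defence is that the SAP is doing its job. Protocol 9.2 leaves technical detail to the SAP, the RECIST appendix (Protocol 10.12) says the analysis plan must address missing assessments when response is determined, the removal paragraph is framed as practical guidance, and SAP 1 denies only major changes. This supports a SAP rule for deriving BOR. It does not support taking a documented PD out of a response denominator. It is also fair that SAP 3.2.4 already tabulates non-evaluable BOR with its reason in the all-treated population, so a careful reader could trace these participants.

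Four stronger readings are tempting and are not supported.

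- A reader might infer that the documents are silent on who the 20 are. They are not: Protocol 9.3 and SAP 3.8 name the activity population, while Protocol 9.4 and SAP 4 gloss evaluability more broadly. This is a conflict left unreconciled. The gloss's silence on measurable disease has little practical effect, because inclusion criterion I 07 requires it.
- A reader might infer that the DCR must rise. That depends on the SAP's SD minimum.
- A reader might infer that on-time week-16 progressors will be removed. That lets the parenthesis override the rule it explains; the wording is loose, no more.
- A reader might infer that clinical progression without a scan keeps a participant in while an early SD scan followed by clinical progression takes one out. If the early scan is itself treated as non-evaluable, the second sentence of Table 3 brings that participant back.

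**Conclusion.** The point holds for the supplementary analyses. SAP 2 narrows a protocol-defined population, does not declare it, and does so in a way that can only hold or raise the activity-set ORR and, under the SAP's own rules, the DCR. The effect is probably small. In the illustration ORR moves by at most 1.8 points (21.1% to 22.9%), against a 95% exact interval of 9.6% to 37.3% for 8/38; DCR moves by up to 5.4 points (63.2% to 68.6%). Both rest on the assumed 1 to 3 removals. Group (a) looks narrow, since it needs a scan before day 42, such as an end-of-treatment scan after a single dose, and nothing evaluable afterwards.

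It would be wrong to conclude that the primary result or the futility boundary is biased. The all-treated ORR keeps these participants as non-responders, and the 0 or 1 of 20 threshold does not move on either reading. The interim count is affected only under narrowed selection with replacement. The change is worth making because the effect runs one way, the set feeds an enrollment decision, and the correction is cheap.

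**What to change.** - In SAP 2, delete the exclusion for the activity population. Keep these participants in the denominator as non-responders for the activity-set ORR and DCR and for the interim count, and show BOR as non-evaluable with the reason, as SAP 3.2.4 already plans for the all-treated population.
- In SAP 3.8, state that the Table 7/Table 3 activity definition selects the first 20, and align the evaluability wording in SAP 4.
- If a missed-scan rule is kept for deriving BOR, declare it in SAP 3.9 and make its date test allow for the ±7-day scan window, so that it applies only after day 119. The PFS censoring rule can stay as it is.
- Minor, and affecting timing only: the interim cut-off refers to leaving the study in Protocol 9.3 and SAP 3.8 but to stopping study treatment in the Protocol 1.1 synopsis. Reconcile the two.

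The cost is one paragraph in SAP 2, one sentence in SAP 3.8 and matching words in SAP 4, best made before the interim count. It needs no new data and does not touch the threshold or the primary analysis. Protocol 9.3 and 9.4 can be aligned at the next amendment.
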